## **Specific adverse events**

### Adverse Events leading to permanent discontinuation of study drug

- Source: Adverse Events CRF / Infections CRF/CMV CRF
- Occurrence: “Action taken” = 2 (“Study drug permanently discontinued due to this adverse event/infection”)

### Infections

- Source: Adverse Events CRF / Infections CRF/CMV CRF
- Occurrence: Infections are all treatment emergent adverse events with MedDRA SOC = 10021881 (Infections and infestations) or events verified as infections after medical review (not necessarily coded as “Infections and infestations”).

### **5.1.4 Target therapeutic ranges**

#### **Everolimus**

Target therapeutic ranges for Everolimus whole blood trough levels should be 5 – 10 ng/mL.

#### **Cyclosporin A**

Target therapeutic range for Cyclosporin A whole blood levels should be the following:

From Month 3 up to Month 6: 100 – 200 ng/mL. After Month 6: 50 – 150 ng/mL.

In the CNI-free group the Cyclosporin A will be reduced to a dose resulting in a C0 level of  $\leq$  75 ng/mL starting at Month 6 post Tx and finally (after 8 weeks of reduced dosage) removed completely. At the latest at Month 9, Cyclosporin A should be withdrawn completely from the immunosuppressive regimen in the CNI-free group.

#### **Tacrolimus**

Target therapeutic range for Tacrolimus whole blood levels should be the following:

From Month 3 up to Month 6: 5-10 ng/mL. After Month 6: 3-8 ng/mL.

In the CNI-free group the Tacrolimus will be reduced to a dose resulting in a C0 level of  $\leq$  5 ng/mL starting at Month 6 post Tx and finally (after 8 weeks of reduced dosage) removed completely. At the latest at Month 9, Cyclosporin A or Tacrolimus should be withdrawn completely from the immunosuppressive regimen in the CNI-free group.

## **5.2 Imputation rules**

### **5.2.1 Study drug**

In case of missing or partial start date, the start date should be shifted to earliest possible date, but not earlier than the Screening visit. Missing or partial end dates should be shifted as far back as possible but not later than the last known date subject took study drug (from Study Completion CRF).

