At Month 6 (± 1 week) post transplantation (Baseline), patients whose eligibility is confirmed by additional in- and exclusion criteria will be randomized and hence allocated to one of the two treatment groups in a 1:1 ratio. Patients will then either receive an immunosuppressive regimen consisting of a CNI (Tacrolimus or Cyclosporin A) with Everolimus with corticosteroids or be switched to the CNI-free regimen in the following way:

Starting the day following the Month 6 assessment, Cyclosporin A will be reduced to ≤ 75 ng/mL (according to C0 level) or Tacrolimus will be reduced to ≤ 5 ng/mL (according to C0 level) for 8 weeks and subsequently removed completely. Depending on the initial immunosuppression either MPA or Everolimus will be added to the patient's immunosuppressive regimen. Consequently, patients receive a transitional immunosuppressive regimen of Cyclosporin A or Tacrolimus and Everolimus and MPA or MMF until complete switch to the CNI-free regimen is achieved at 9 months post Tx.

Dose increase / adjustment of MPA should be performed based on the investigator's experience and the given clinical conditions, adverse events, etc. The CNI-free regimen should be achieved after a maximum of 3 months and be stable by Month 9. During the therapy-switch a control assessment will be performed at Month 8.

In all patients, further control assessments will be performed at Month 9, 10, 12 and 18 (end of study and early discontinuation) post Tx.

[figure not shown]
Corticosteroids must be added to the immunosuppressive regimen in all patients, according to local standard. A dose of 0.05 – 0.3 mg/kg prednisolone or equivalent should be continued throughout the whole study.

Obligatory biopsies will be obtained at Month 6, 9, 12, 18. Facultatively biopsies may be obtained at every study visit.

Statistical analysis and report writing will be performed when all patients have completed Month 18 after Tx assessment.

An external and independent Data Safety Monitoring Board (DSMB) will be instituted. The DSMB will review safety-related issues and will be entitled to make recommendations for changes in study conduct. Details on the function of the DSMB will be laid out in a separate DSMB Charter.

Table 4-1 Study outline

Patients should be seen for all visits on the designated day or as close to it as possible.

Baseline visit assessments and randomization (Month 6 post Tx) may be performed within a time window of \pm 1 week.

5 Population

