6.5 Treating the patient

6.5.1 Study drug administration

Everolimus is study drug from month 3 (visit 1). Before month 3 the patient will receive a prescription for Everolimus, the use of Everolimus before visit 1 is not excluded. Each study site will be supplied by Novartis with study drug (Everolimus). Study drug will be provided as tablets, packaged in boxes containing strips of blister packed tablets, and labeled as RAD001 Tablets. Study drug will be available in 0.25, 0.75, and 1.0 mg strength. One component of the box consists of a 2-part label which includes an identifier of each single box of study medication. Before dispensing the study medication to an individual patient, investigator staff must enter the 4-digit patient number and the date of dispensing of the medication box on both parts of the label. The outer part of the label will be detached from the packaging and affixed to the source document (Drug Label Form in the CRF) containing that patient's unique patient number.

For the other immunosuppressive drugs (Cyclosporin A, Tacrolimus, MPA, corticosteroids) the patient will receive a prescription.

The prescribed total daily dosage of the immunosuppressive drugs should be divided in two (equal) doses, applied 12 hours apart (i.e. 08:00 a.m. and 08:00 p.m.).

The investigator should instruct the patient to take the study drug exactly as prescribed in order to promote compliance. All dosages prescribed and dispensed to the patient and all dose changes during the study must be recorded on the Dosage Administration Record CRF.

In patients randomized to the CNI-free group, withdrawal of Cyclosporin A or Tacrolimus and commencement of MPA or Everolimus will be performed starting the day after randomization at Month 6 post Tx.

In a first step the Cyclosporin A should be decreased to a dose resulting in a C0 blood level of \leq 75 ng/mL for 8 weeks, and Tacrolimus should be decreased to a dose resulting in a level of \leq 5 ng/mL. MPA or Everolimus should be introduced. Further increase / adjustment of MPA or Everolimus and removal of Cyclosporin A or Tacrolimus should be performed based on the investigator's experience and the given clinical conditions, adverse events, etc. The CNI-free regimen should be achieved after a CNI reduction / elimination period of maximum of 3 months (starting from Month 6 post Tx and be stable by Month 9 post Tx).

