Sexually active men (including vasectomized men) are recommended to use condoms during treatment and for at least 90 days after cessation of treatment. In addition, female partners of male patients treated with MPA are recommended to use highly effective contraception during treatment and for a total of 90 days after the last dose.

Men should not donate semen during therapy with MPA or for 90 days following discontinuation of MPA.

Table 6-1 Schematic diagram of medication administration

Phase	No Study	Prephase	Study Drug Treatment						
			Run In	BL	Switch	Maintenance			
Visit		1	2	3	4	5	6	7	
Month post Tx	0 - 3	3	6	8	9	10	12	18	
Randomization			X						

Treatments				
CNI group				
- Everolimus		center practice	C0-h level: 5 – 10 ng/mL	
- CNI (Cyclosporin A/ Tacrolimus)		acc. to blood level *	acc. to blood level *	acc. to blood level *
- MPA		center practice	none	None
- Steroids		0.05 – 0.3 mg/kg	0.05 – 0.3 mg/kg Prednisolone or equivalent	
CNI-free group				
- Everolimus		center practice	C0-h level: 5 – 10 ng/mL	
- CNI (Cyclosporin A/Tacrolimus)		acc. to blood level *	CyA: C0 level of ≤ 75 ng/mL for 8 weeks, then removal Tac: C0 level of ≤ 5 ng/mL for 8 weeks, then removal	None

- MPA		center practice	MMF 1.5 – 3 g/d OR EC-MPS 1440 – 2880 mg/d	MMF 1.5 – 3 g/d OR EC-MPS 1440 – 2880 mg/d
- Steroids		0.05 – 0.3 mg/kg	0.05 – 0.3 mg/kg Prednisolone or equivalent	

BL

= Baseline visit: day of randomization – Month 6 post Tx

CNI Group: treatment post randomization: Everolimus + Cyclosporin A/Tacrolimus + corticosteroids

Cyclosporin A Dosage: Month 1 - 6: C0-h levels 100 – 200 ng/mL
Month >6: C0-h levels 50 – 150 ng/mL
(cf. section 6.5.2)

Tacrolimus Dosage: Month 1 - 6: C0-h levels 5 - 10 ng/mL
Month >6: C0-h levels 3 - 8 ng/mL

CNI-free Group: treatment post randomization: Everolimus + MPA + corticosteroids

Cyclosporin A Dosage: Month 1 - 6: C0-h levels 100 – 200 ng/mL
Month 6 - 9: C0-h levels ≤75 ng/mL
(cf. section 6.5.2)

Tacrolimus Dosage: Month 1 - 6: C0-h levels 5-10 ng/mL
Month 6 - 9: C0-h levels ≤5 ng/mL

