In the CNI-free group the Tacrolimus will be reduced to a dose resulting in a C0 level of ≤ 5 ng/mL starting at Month 6 post Tx and finally (after 8 weeks of reduced dosage) removed completely. At the latest at Month 9, Cyclosporin A or Tacrolimus should be withdrawn completely from the immunosuppressive regimen in the CNI-free group.

If Tacrolimus medication is interrupted for safety related considerations for more than 4 consecutive weeks or more than 8 cumulative weeks after randomization, discontinuation of the medication should be considered and the patient should be withdrawn from study treatment. Appropriate information needs to be recorded on the Dosage Administration CRF.

The co-administration of drugs known to interfere with Tacrolimus metabolism should be avoided if possible. If these drugs are required, the investigator must monitor Tacrolimus and/or Everolimus trough levels (Appendices 3 and 4).

Mycophenolic Acid (MPA)

In patients randomized to the CNI-free group, treatment with MPA will be introduced starting the day after Baseline (Month 6 post Tx) assessment (see [section 6.5.1](#)). Either Mycophenolate Mofetil (MMF) or Enteric-Coated Mycophenolate Sodium (EC-MPS) may be applied.

In case of leukopenia (leukocyte count $< 3,000/\text{mm}^3$), neutropenia (neutrophil count $< 1,500/\text{mm}^3$), or anemia, MPA medication doses may be reduced at the discretion of

the investigator or eliminated completely until the event resolves. Furthermore, for any other moderate/severe AE which in the opinion of the investigator warrants a dose reduction or temporary interruption of the medication, this will be allowed. However, the MPA medication should be restarted once the AE has resolved or returned to an acceptable grading (see instructions given in [Appendix 5](#)).

If MPA medication is interrupted for safety related considerations more than 2 weeks during the run in phase (Month 3 to Month 6 post Tx) or for more than 4 consecutive weeks or more than 8 cumulative weeks, discontinuation of the medication should be considered and the patient should be withdrawn from study treatment. Appropriate information needs to be recorded on the Dosage Administration CRF.

The Month 18 assessments will be performed and documented for all patients who are withdrawn prematurely from the treatment at timepoint of discontinuation and again at month 18 after Tx.

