### **2.1.1 General definitions**

#### Study drug:

The term “Study drug” refers to any drug administered to the patient as part of the required study procedures.

Certican®/ Everolimus was investigational drug. Sandimmun®Optoral/Cyclosporin A, Prograf®/Tacrolimus and MPAs (Myfortic®/EC-MPS or CellCept®/MMF) were considered as study drug as well. Corticosteroids were handled in the same way as concomitant medication.

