## **2.4 Treatments (study treatment, rescue medication, concomitant therapies, compliance)**

### **2.4.1 Study treatment / compliance**

Duration (days) of Everolimus application were summarized. Dose interruptions, i.e. days with dose of 0 mg were considered for calculation of duration. Daily Everolimus dose levels were summarized with mean, standard deviation, minimum, median, and maximum by visit. Dosage averages were calculated including and excluding zero doses for periods of temporary interruption of study medication regardless of whether this was due to safety reasons or patients' non-compliance. Assignment of the DAR records to the visits were calculated based on the visit dates. Reasons for dose adjustments (including temporary dose interruption) were presented by frequency distribution. These frequencies of dose reduction (including temporary dose interruption) for safety reasons as per protocol guidelines were presented by study period. Permanent treatment discontinuations were analyzed by frequencies.

These analyses were performed per treatment group, for the SAF population and related to the study periods in the randomized treatment period (see section 2.1 Data analysis general information). For the run-in period, duration and mean daily dose were summarized for the ENR population displaying both, randomized versus not randomized patients as well as the initial treatment groups CNI+MPA versus CNI+ Everolimus

Daily Cyclosporin A and Tacrolimus doses adjusted by the patients' visit-specific body weight and MPA doses were summarized by visit and in the same way as Everolimus. Data were presented separately for each treatment group. Induction therapy (Basiliximab or ATG or no induction) received by patient was summarized by treatment group, for the SAF population. The distribution of the specific CNI medications was summarized by treatment group.

Duration (days) of treatment with Cyclosporin A, Tacrolimus, MPA, and steroids as well as frequency of Cyclosporin A, Tacrolimus and MPA dose adjustments (including temporary dose interruption) for safety reasons as per protocol guidelines were determined. Reasons for dose adjustments (including temporary dose interruption) were presented by frequency distribution. Permanent treatment discontinuations were analyzed using frequency distribution. All other immunosuppressive therapies were summarized by ATC (Anatomical, Therapeutic, Chemical) classes.

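### SAP 5.2.1 uses Screening as the only floor for incomplete study-drug start dates, so MPA or everolimus introduced after randomization can be imputed into the run-in

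*SAP*

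**What the plan says.** SAP 5.2.1 has one rule for a missing or partial study-drug start date: "the start date should be shifted to earliest possible date, but not earlier than the Screening visit". SAP 2.1.1 names everolimus as investigational drug and adds that cyclosporin, tacrolimus and MPA count too ("MPAs (Myfortic®/EC-MPS or CellCept®/MMF) were considered as study drug as well"), so the rule covers all of them.

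The run-in regimen is a CNI with either everolimus or MPA, plus steroids (Protocol 4 and 6.2). For the CNI-free group, Protocol 4 states: "Depending on the initial immunosuppression either MPA or Everolimus will be added to the patient's immunosuppressive regimen". Protocol 6.5.1 gives the timing: "commencement of MPA or Everolimus will be performed starting the day after randomization at Month 6 post Tx". Protocol 6.5.2 repeats it for MPA: "treatment with MPA will be introduced starting the day after Baseline (Month 6 post Tx) assessment". The notes to Protocol Table 6-1 give the other arm: "CNI Group: treatment post randomization: Everolimus + Cyclosporin A/Tacrolimus + corticosteroids". A CNI-group patient who entered on CNI+MPA therefore also starts everolimus after Month 6.

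SAP 2.4.1 summarizes run-in duration and mean daily dose by randomization status "as well as the initial treatment groups CNI+MPA versus CNI+ Everolimus". It assigns dose records to visits by comparing dates, and it summarizes MPA in the same way as everolimus.

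**The concern.** Screening is a sensible floor for a drug that the patient was already taking in the run-in. For a drug that by design first appears after Month 6, it is about three months too low. Every date between Screening and randomization contradicts the treatment sequence, yet the rule picks such a date whenever the known date parts allow it.

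At stake are the run-in exposure tables. A CNI+everolimus entrant allocated to CNI-free treatment could show run-in days on MPA. A CNI+MPA entrant in either arm could show run-in days on everolimus. If the initial regimen groups were built from the same derived dates, such a patient would fit both groups or neither.

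**Working it through.** The plan states no figure to reproduce, so the check applies the rule literally.

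**Inputs**
- Imputed start = the later of (earliest date compatible with the known parts) and (Screening), from SAP 5.2.1.
- True start = randomization + d days. The protocol's earliest time is d = 1 (Protocol 6.5.1). Larger d is varied as an assumption.
- Screening is Month 3 ± 2 weeks and Baseline is Month 6 ± 1 week (Protocol 4). The run-in is nominally 91 days, with a range of 91 ± (14 + 7) = 70 to 112 days.
- Randomization dates are assumed to be spread evenly over the calendar.

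**Day missing, month and year known.** The imputed date is the 1st of the month. If the true start is day D of the month, the shift is D − 1 days. The imputed date precedes randomization when D − 1 > d, so a month of m days contributes max(m − d − 1, 0) such dates. A four-year cycle has 48 months: 28 of 31 days, 16 of 30, three of 28 and one of 29, in total 1,461 days.

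| True start after randomization | Dates imputed before randomization | Share |
|---|---|---|
| d = 1 | 1,461 − 48 × 2 = 1,365 | 93.4% |
| d = 7 | 1,461 − 48 × 8 = 1,077 | 73.7% |
| d = 14 | 1,461 − 48 × 15 = 741 | 50.7% |
| d = 28 | 28 × 2 + 16 × 1 = 72 | 4.9% |

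Mean shift = Σ m(m − 1)/2 ÷ 1,461 = (28 × 465 + 16 × 435 + 3 × 378 + 406) ÷ 1,461 = 21,520 ÷ 1,461 = 14.7 days. The maximum is 30. For d = 1, the false run-in days average 13.8, with a maximum of 29. Screening lies at least 70 days before randomization, so a day-missing date never reaches that floor.

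**Only the year known, d = 1, 91-day run-in.** Screening is 92 days before the true start. If the true start is day Y of a 365-day year, the shift is min(Y − 1, 92).
- Mean shift = (0 + 1 + … + 91 + 273 × 92) ÷ 365 = (4,186 + 25,116) ÷ 365 = 80.3 days.
- The imputed date precedes randomization when Y ≥ 3: 363 ÷ 365 = 99.5%. It lands exactly on Screening in 273 ÷ 365 = 74.8%.
- False run-in days average 79.3 (63.0 for a 70-day run-in, 94.4 for 112 days).
- A later true start matters little here. The share before randomization is (365 − d − 1) ÷ 365, which is 95.9% at d = 14 and 92.1% at d = 28.

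**Date wholly missing.** The start is always set to Screening. That gives 91 false run-in days (70 to 112), whatever the value of d.

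**With a floor at the day after randomization.** The imputed start is the later of the earliest compatible date and randomization + 1. No run-in day is created in any of these cases.

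**The case against.** A strong defence can be made on five grounds.

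1. **The regimen is recorded elsewhere.** Immunosuppression taken at Month 3 is recorded at Visit 1 and changes at Visit 2 (Protocol 7). A reader might infer that the rule misrecords a patient's run-in regimen. The documents do not support that: imputation alters a derived date, not the CRF entry, and the SAP does not say that the initial groups come from imputed dates. This stands.

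2. **The 93% depends on a start exactly one day after randomization.** The protocol gives that day as the beginning of introduction and leaves further adjustment to the investigator within a switch of up to three months. A reader might infer that nearly every incomplete date lands in the run-in. For day-missing dates the table above shows otherwise. This stands.

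3. **Few or no dates may be affected.** Protocol 6.5.2 and 7.4 require dates for immunosuppressive therapy and its changes, Protocol 9.3 sends omissions back to the site as queries, and the drug is introduced at a scheduled visit. This stands: the count is unknown and may be zero.

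4. **Longer total exposure is not reported as such.** Summaries are by study period, and SAP 5.1.1 lists no pooled Screening-to-Month-18 period. With d = 1, backdating adds at most about one day to the randomized period. This stands.

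5. **Both drugs may have been taken in some run-ins.** Protocol Table 6-1 lists everolimus and MPA there as center practice, although Protocol 6.2 says one or the other. Genuine combined use cannot be excluded for every patient, so the fix must not erase it.

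None of this supplies the missing bound. No section sets a floor at randomization or separates run-in drugs from those introduced later.

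**Conclusion.** The point holds as a small gap in a descriptive derivation. As written, the rule can date a post-randomization drug into the run-in, which produces false run-in duration and dose in the SAP 2.4.1 summaries.

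The error per affected record is about two weeks when only the day is missing and the drug started the day after randomization. It is close to the whole run-in when the month is also unknown. For day-missing dates it shrinks quickly as the true start moves later. The overall effect cannot be sized, because the documents do not say how many dates are incomplete. Blurring of the two initial regimen groups is conditional on their being derived from imputed dates, which the SAP leaves open.

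A reader might infer a threat to the trial's conclusions. There is none from this source: the primary ANCOVA uses randomized group, center and baseline GFR (SAP 2.5.2), and event times run from randomization to the event (SAP 2.6.2). Neither uses study-drug start dates.

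**What to change.** Add to SAP 5.2.1:

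> *For a study drug that the immunosuppression records do not show as taken between Screening and randomization (a drug newly prescribed at Visit 2 because of the randomized allocation does not count as taken), an incomplete start date is not set earlier than the day after randomization. For drugs taken in the run-in the floor remains the Screening visit. The initial regimen group is taken from the recorded run-in medication, not from imputed dates.*

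The clause in brackets is needed because Visit 2 is also the randomization visit, so a drug prescribed there could otherwise be read as run-in medication. Patients who are recorded on both drugs in the run-in are left as they are. A listing of all imputed study-drug start dates would show how many records are involved.

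The cost is one short SAP paragraph and one programming condition, using medication records already collected at Visits 1 and 2. No treatment rule changes.

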### **5.2.2 AE date imputation**

In case of missing or partial start date or end date of an AE, the start date should be shifted to the earliest possible date, but not earlier than the first intake of study drug while the end date should be shifted as far back as possible.

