9. Venous blood will be drawn for measurement of the C0-h levels of Cyclosporin A or Tacrolimus and Everolimus.
10. Venous blood will be drawn for frozen storage until end of trial (2 EDTA-tubes, **2-5 mL**).
11. In woman of childbearing potential a pregnancy test will be performed (β -HCG).
12. Urinalysis for proteinuria will be performed (spot urine sample for protein/creatinine ratio may be used).
13. Changes in Concomitant medications / significant non-drug therapies will be recorded.
14. (Changes in) immunosuppressive medication will be recorded.
15. Information on rejection episodes, hemodynamic compromise, MACE, hospitalization, infections, and other (S)AEs that occurred since the last visit will be recorded.

Switch of immunosuppressive regimen - Visit 3 (Month 8 post Tx)

This visit may be performed within a time window of \pm 1 week.

1. Vital signs will be measured.
2. Venous blood will be drawn for measurement of hematology and biochemistry.
3. In woman of childbearing potential a pregnancy test will be performed (β -HCG).
4. Venous blood will be drawn for measurement of viral serology (CMV status including pp65 Ag)
5. Venous blood will be drawn for measurement of
 - Everolimus C0-h level in all patients
 - Cyclosporin A C0-h level, only in patients of the CNI group

- Tacrolimus C0-h level, only in patients of the CNI group
- 6. Changes in concomitant medications / significant non-drug therapies will be recorded.
- 7. Changes in immunosuppressive medication (including study drug dosage) will be recorded.
- 8. Information on rejection episodes, hemodynamic compromise, MACE, hospitalization, infections, and other (S)AEs that occurred since the last visit will be recorded.

Maintenance Period - Visits 4, 5 and 6 (Month 9, 10, 12 post Tx)

These visits may be performed within a time window of \pm 1 week.

- 1. Vital signs will be measured.
- 2. An endomyocardial biopsy will be performed (only visits 4 and 6).
- 3. A 12-lead ECG will be written (not at month 10, Visit 5).
- 4. Venous blood will be drawn for measurement of hematology and biochemistry.
- 5. Venous blood will be drawn for the measurement of viral serology (only CMV-status including pp65 Ag).
- 6. Venous blood will be drawn for measurement of
 - Everolimus C0-h level in all patients
 - Cyclosporin A C0-h level, only in patients of the CNI group
 - Tacrolimus C0-h level, only in patients of the CNI group

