#### Date of first administration of study drug:

“Date of first administration of study drug” is defined as the first intake of study medication which should start within 5 days preceding the Screening visit and be documented on the Everolimus therapies CRF.

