## **2.7 Safety analyses**

### **2.7.1 Adverse events (AEs)**

Safety variables were analyzed separately

- for the period between Screening and Baseline (run-in period)
- for the period between Baseline and Month 9 (switch period)
- for the period between Month 9 and Month 18 (maintenance period)
- for the period between Baseline and final assessment (Month 18 or date of premature withdrawal from the study) (randomized treatment period),.

For the randomized treatment period, analyses of treatment emergent adverse events were performed according to the treatment group into which the patients were randomized.

All analyses of safety parameters were based on the safety population. For the period between Screening and Baseline visit summaries of all adverse events were displayed for the ENR population by randomization status, i.e. randomized versus not randomized patients.

The key safety variables which were analyzed are as follows.

- Incidence and severity of infections, in particular clinically apparent CMV
- Incidence and severity of Adverse Events (AEs) and Serious Adverse Events (SAEs)
- Incidence of AEs leading to discontinuation from the study
- Relative frequency of abnormal vital signs measurements and laboratory parameters

The incidence rates for (serious) adverse events and infections were analyzed by treatment group.

AEs/Infections:

Generally, infections data were analyzed together with AE data. In addition, infection data were analyzed separately.

Data collected by AE CRFs and by Infection CRFs and CMV-CRFs were coded with the MedDRA dictionary that gives preferred term and body system information. The incidence of AEs were summarized by body system, preferred term, severity, and relationship to study drug. All information pertaining to AEs noted during the study were listed by treatment group and patient, detailing verbatim given by the investigator, the preferred term, the body system, start/end dates, severity and drug relatedness. The AE onset was also shown relative (in number of days) to the day of initial dose per study period (within the first 3 months, after Baseline (Month 6)).

In addition to being analyzed similarly as AEs, as described above, the relative frequency of infection by type and micro-organism was tabulated. AEs occurring 30 or more days after the discontinuation of study medication were not included in AE/infection summary tables.

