#### **5.2.3.1 Prior therapies date imputation**

In case of missing or partial start date or end date of a prior therapy, the dates should be shifted to the earliest possible date, but not earlier than the first intake of study.

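### The AE start-date imputation rule (SAP 5.2.2) has no randomization-date floor, so post-randomization AEs with missing and some partial start dates can be assigned to the run-in.

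*SAP*

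**What the plan says.** SAP 5.2.2 covers missing and partial AE dates: "the start date should be shifted to the earliest possible date, but not earlier than the first intake of study drug". No other lower limit is given.

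SAP 2.1.1 defines first administration as "the first intake of study medication which should start within 5 days preceding the Screening visit", to be "documented on the Everolimus therapies CRF". Screening is at Month 3 and randomization at Month 6. The same section says that cyclosporin A, tacrolimus and MPA "were considered as study drug as well".

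SAP 5.1.1 separates the run-in (Month 3 to 6) from the randomized treatment period (Month 6 to 18), which is split into switch and maintenance at Month 9. Under SAP 2.7.1, treatment-emergent AEs are analysed by randomized arm "for the period between Baseline and final assessment (Month 18 or date of premature withdrawal from the study"). Run-in AEs are shown by randomization status, not by arm.

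Protocol section 7 (Visit 3, and likewise later visits) has sites collect information so that "other (S)AEs that occurred since the last visit will be recorded".

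For prior therapies, SAP 5.2.3.1 uses a similar floor: "the dates should be shifted to the earliest possible date, but not earlier than the first intake of study".

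**The concern.** Dating an uncertain AE as early as possible, but not before first dose, is cautious when first dose and randomization coincide, because the AE then counts as on treatment. Here they are about three months apart. The same rule can place an AE that began after randomization in a period where the arms are not compared.

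Infections, AEs and SAEs are named as key safety variables in SAP 2.7.1, so what is at stake is the completeness of the by-arm safety tables. For dates lacking only the day, the affected AEs are those that began in the calendar month of randomization. That is when the CNI-free arm starts its switch.

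**Working it through.** The documents give no number or rate of incomplete AE dates, so there is no planned figure to reproduce. What can be calculated is the share of truly post-randomization AEs that the rule would date before randomization, by type of incompleteness.

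**Inputs from the SAP.** Imputed start = the later of (first intake *f*, earliest date compatible with the known parts), from 5.2.2. First intake is at about Month 3 (2.1.1) and randomization *r* is at Month 6.

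**Assumptions, not in the documents.** *f* = *r* − 91 days. Randomization is spread evenly over calendar days. True onset is uniform over the *T* days after *r*, with *T* = 365 (Months 6-18), 91 (Months 6-9) or 30.

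1. **Start date wholly missing.** Imputed start = *f* = *r* − 91, so 100% fall before randomization.
2. **Only the year known.** The AE moves to 1 January of its year, or to *f* if later. It falls before *r* when onset is in the calendar year of randomization and *r* is not 1 January.
   - *T* = 365: on average 364/2 = 182 days of the year remain, and 182/365 = 49.9%. Removing the 1 January case (1/365 = 0.3%) leaves about 49.6%.
   - *T* = 91: 1 − ((91 + 1)/2)/365 = 1 − 46/365 = 87.4%. Less 0.3%, this is about 87.1%.
   - A simulation of 200,000 AEs gave 49.6% and 87.0%.
3. **Only the day missing.** The AE moves to day 1 of its own month, so it falls before *r* only if onset is in the randomization month and *r* is not day 1. With an average month of *m* = 365.25/12 = 30.4 days, the mean number of exposed days is (*m* − 1)(*m* − 2)/(2*m*) = 29.4 × 28.4/60.8 = 13.7.
   - *T* = 365: 13.7/365 = 3.8%.
   - *T* = 91: 13.7/91 = 15.1%.
   - *T* = 30: 13.7/30 = 46%.
   - The simulation gave 3.8% and 15.2% for the first two.
   - If randomization on day 1 also counts (imputed start equal to *r*), the exposed days are (*m* − 1)/2 = 14.7. The shares become 4.0%, 16% and 49%.
4. **Month known and later than the randomization month.** Day 1 of that month is after *r*, so 0% move.

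**Patients run in on CNI + MPA.** Protocol section 4 allows this run-in and SAP 2.4.1 tabulates the group. Everolimus may then start only after randomization.

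| Reading of first intake | Floor for these patients | Consequence |
|---|---|---|
| Any study drug (2.1.1, definition of study drug) | about Month 3 | As in steps 1-4 |
| Everolimus CRF (2.1.1, date of first administration) | could be after Month 6 | A wholly missing date lands in the randomized period, and a poorly dated run-in AE could be moved into it |

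The SAP does not settle which reading applies.

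**The case against.** **Visit of report.** An AE recorded at Month 8 as new since the previous visit could not have begun at Month 3, so a sensible programmer would not date it there. The SAP also leaves the earliest possible date undefined and has no written rule assigning AEs to periods by imputed start. Both observations are fair. But the visit of report is not part of 5.2.2, and the only limit stated there is first intake. A programmer who follows the text gets the misassignment.

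**Data cleaning.** Start and end dates are collected for AEs and infections (Protocol 7.6), omissions are queried (9.3), and SAE documentation is fully source-verified (9.1). This stands as a reason to expect few incomplete dates. It does not correct the rule for those that remain.

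**Stronger readings that a reader might infer.**
- *Every incompletely dated AE goes back to Month 3.* It does not: the known month or year limits the shift.
- *The rule can only remove AEs from the randomized period.* This fails if first intake means first everolimus in patients run in on CNI + MPA.
- *The comparison between arms is biased.* The rule is the same in both arms. A biased difference would need incompleteness, or its timing, to differ by arm, and the documents do not show that.
- *Prior therapies are turned into concomitant ones.* SAP 5.2.3.1 applies to records already classed as prior, and nothing says they are reclassified. The floor is illogical, but no effect on a result is shown.

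**Conclusion.** The point holds in a limited form. SAP 5.2.2 has no randomization-date floor. With first intake at about Month 3, post-randomization AEs are dated at or before randomization as follows:

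- no start date: all of them;
- year only: about half, rising to about 87% for onset in Months 6-9;
- day missing only: about 4%, rising to about 15% for Months 6-9 and 46-49% for the first 30 days.

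These shares rest on uniform onset and a 91-day gap, and on periods being assigned by imputed start date, which the SAP implies but does not state. They are shares of incompletely dated AEs, not of all AEs. The total is unknown and may be small.

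The main consequence is under-counting in the randomized-period safety tables. The primary GFR analysis is not touched. For patients run in on CNI + MPA, even the position of the floor is unsettled.

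**What to change.** In SAP 5.2.2:

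- For randomized patients, when the recorded date parts, the end date and the visit of first report do not show onset before randomization, impute the later of the earliest compatible date and the randomization date.
- Keep the first-intake floor for non-randomized patients, who have no randomization date, and for AEs shown to have started before randomization.
- Define first intake once, as any study drug, and align SAP 2.1.1 with it.

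As a minor consistency correction, remove the first-intake floor for prior therapies in SAP 5.2.3.1.

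With this floor, no post-randomization AE without evidence of earlier onset is dated before randomization. The cost is SAP wording and a few lines of code. The downside is small: a few poorly dated run-in AEs may be counted after randomization, by the same rule in both arms.
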